Cognitive Reappraisal Intervention for Suicide Prevention (CRISP): An Intervention for Middle-Aged and Older Adults Hospitalized for Suicidal Ideation or Suicide Attempt

Weill Cornell Medicine; NCT 03026127

Operations Manual
June 2020

Sponsored by the National Institutes of Health (NIH)

BACKGROUND

Suicide rates in middle-aged and older adults are alarmingly high, and suicide risk increases for those who have been hospitalized for suicidal ideation or suicide attempt. Reducing suicide rates in at-risk populations is a major NIMH priority. To address this need, we developed Cognitive Reappraisal Intervention for Suicide Prevention (CRISP) to help middle-aged and older adults (50 years old and older) reduce their suicide risk after a suicide- related hospitalization.

CRISP draws on recent advances in affective neuroscience and aims to improve cognitive reappraisal ability (i.e. the ability to modify the appraisal of a situation to alter its emotional significance) and reduce suicide risk. Our conceptual framework is based on the premises that: a) suicidal ideation and behavior are associated with unsuccessful attempts to regulate intense negative emotions, including depression, anxiety, hopelessness, irritability, anger, and guilt; b) cognitive reappraisal is an effective emotion regulation strategy with identified and investigated neurobiological correlates; c) decreased cognitive reappraisal is associated with increased suicide risk; and d) cognitive reappraisal strategies can be effectively used to reduce suicide risk in our population. We place emphasis on suicidal ideation, in addition to suicidal behavior, because suicidal ideation after a suicide-related hospitalization is a known significant risk factor for suicide. CRISP also employs environmental adaptations/aids to assist patients in utilizing CRISP techniques between sessions (WellPATH personalized tablet app, written step-by-step plan, phone calls). We focus on the first 3 months post-discharge from a suicide-related hospitalization, a period of high suicide risk.

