Behavioral interventions for middle-aged and older adults with depression and suicidal ideation are scarce. This project aims to meet the needs of middle-aged and older adults who have been discharged after a hospitalization for suicidal ideation or suicide attempt with any depression or anxiety disorder. We exclude bipolar patients in mixed, hypomanic, or manic state, and patients with psychosis or dementia. Regulation of emotions associated with mixed, hypomanic and manic state may need different techniques than those covered in CRISP.

Consistent with the NIMH *Strategy 3.1*, CRISP is a novel intervention on a mechanism of action, cognitive reappraisal, to reduce suicide risk. In response to NIMH *Strategy 4.3*, The WellPATH app is an innovative tablet application with personalized cognitive reappraisal techniques to improve cognitive reappraisal and potentially reduce suicide risk. Finally, CRISP's use of cognitive reappraisal, application to cross-diagnostic categories and use of two different levels of analysis are consistent with NIMH's RDOC initiative.

Middle-aged and older adults, who have been hospitalized for suicidal ideation or suicide attempt, are an at-risk and understudied population. If effective, CRISP may

decrease suicide risk, reduce depression, and improve quality of life for this vulnerable group.

STUDY AIMS

The goals of the study are:

MONTHS 1-3:

1. Finalize the CRISP Manual and establish feasibility of therapist training. We will train 4 LMSW/LCSWs: 2 will be trained in the CRISP therapy, 2 will be trained in Supportive Psychotherapy. We will determine the success rate of training and number of hours needed to achieve CRISP certification.

MONTHS 4-24:

[figure not shown]
2. Assess CRISP's reach, feasibility and acceptability: We will assess across conditions:
 - a. Reach: Number of patients screened, and those who meet inclusion criteria;
 - b. Feasibility: Number of patients who receive CRISP or ST for mental health care and research procedures (timely referrals, assessments);
 - c. Acceptability: Patient's treatment satisfaction at 6, 12, and 24 weeks.

Benchmarks of the study progress: Feasibility: At least 75% of CRISP participants will complete CRISP. Acceptability: We will obtain treatment satisfaction scores at the end of CRISP treatment.

[figure not shown]

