3. Preliminary Effectiveness: Over the course of 12 weeks, CRISP participants, compared to participants receiving Supportive Psychotherapy will show an improvement in cognitive reappraisal and have greater (effect size) and clinically significant reductions in suicidal risk.

OVERVIEW OF DESIGN

Figure 1.

RESEARCH ASSESSMENTS

Inclusion Criteria:

1. Age equal to or more than 50 years and up to age 90.
2. Any DSM-5 depression or anxiety diagnosis, including major depressive disorder, bipolar depression, depressive disorder Not Elsewhere Classified, anxiety disorder Not Elsewhere Classified, adjustment disorder with anxiety and depressed mood.
3. Hospitalized for suicidal ideation (either active or passive) or suicide attempt; at hospital admission, Columbia Suicide Severity Rating Scale should greater or equal to 3.
4. Mini Mental State Exam more than or equal to 24.
5. English speaking.
6. Capacity to consent.

Exclusion Criteria:

1. Not having Major Depressive Disorder (by SCID, DSM-IV.)
2. Primary Psychotic Disorder.
3. Currently Hypomanic, Manic or Mixed Episode.
4. Diagnosis of Dementia.
5. Active SI to the point they present as a danger to themselves or others.
 - a. *Alert [name] & complete Suicide Risk Assessment.
6. Acute or Severe Medical Illness (i.e., delirium; decompensated cardiac, liver or kidney failure; major surgery; stroke or myocardial infarction during the three months prior to entry).
7. Aphasia, sensory problems and/or inability to speak English.

*Note: Patients on psychotropic medications, opioids or benzodiazepines will be included if they do not meet DSM-5 criteria for opioid, anxiolytics or other substance abuse disorders (Human Subjects).

INTERVENTION

CRISP:

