CRISP utilizes a structured, yet personalized, approach. The goals of CRISP are to use cognitive reappraisal techniques to reduce negative emotions associated with self-harm and to increase involvement in meaningful and pleasurable activities. The CRISP therapist uses the following techniques: identification and evaluation of negative emotions and their relationship with patient's difficulties, suicidal ideation and suicidal behavior (e.g. explore utility of negative emotions and change perspective about trigger) and use of a range of emotion regulation techniques (e.g. situation selection, situation modification, attentional deployment, cognitive reappraisal and response modulation). Environmental aids, including a personalized tablet application are used to augment the CRISP intervention. Finally, at the end of treatment CRISP therapists provide to patients a personalized summary of treatment that highlights the problems that were addressed, and the successful techniques that had been used to solve them.

Comparison Condition: Supportive Therapy:

ST is a control intervention not aimed to improve emotion regulation, including cognitive reappraisal. The ST therapist strives to create a positive alliance with the patient by emphasizing non-specific therapeutic interactions and techniques that convey to the patient, interest, concern and understanding. For the purposes of this study, an effort will be made to avoid all emotion regulation techniques that relate to Cognitive Reappraisal Intervention for Suicide Prevention (CRISP).

FOLLOW-UP ASSESSMENTS

Follow-up assessments are conducted by the WCM research assistant at 6, 12, and 24 weeks after the baseline and include measures of depression and anxiety symptoms, medical burden, and suicidal ideation. Subjects will receive \$50 (cash, check, or gift card) as compensation for completing each assessment. They may also be eligible for up to an additional \$10 for one of the EEG computer tasks.

PROCEDURES FOR TREATMENT AFTER STUDY COMPLETION

Participants whose follow-up assessments indicate a need for continued mental health services will be provided with mental health referrals.

DATA MANAGEMENT

Data will be collected by the study RA at baseline and at follow-up assessments. The RA will also be responsible for writing and presenting patient summaries to the PI. The therapist will complete updates on the progress of their therapy sessions. [name] manages the CRISP database and weekly reporting.

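### Does the follow-up assessment text fail to cover the outcomes set by Aims 2c and 3?

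*Protocol*

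**What the plan says.** Three parts of the Protocol bear on this point.

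- **FOLLOW-UP ASSESSMENTS.** The research assistant sees participants 6, 12 and 24 weeks after baseline, and these assessments "include measures of depression and anxiety symptoms, medical burden, and suicidal ideation". The payment text in the same section then mentions a small extra sum "for one of the EEG computer tasks".
- **STUDY AIMS.** Aim 2c concerns "treatment satisfaction at 6, 12, and 24 weeks", under an introduction that applies Aim 2 to both conditions. The benchmark line below it adds: "We will obtain treatment satisfaction scores at the end of CRISP treatment". Aim 3 states that over 12 weeks CRISP participants, compared with those in Supportive Psychotherapy, "will show an improvement in cognitive reappraisal and have greater (effect size) and clinically significant reductions in suicidal risk".
- **BACKGROUND and Inclusion Criteria.** On the scope of suicide risk, the Background says: "We place emphasis on suicidal ideation, in addition to suicidal behavior". It also refers to the "use of two different levels of analysis" in connection with the RDoC initiative. The only suicide scale named is in inclusion criterion 3: "at hospital admission, Columbia Suicide Severity Rating Scale should greater or equal to 3".

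DATA MANAGEMENT assigns data collection at baseline and follow-up to the research assistant.

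**The concern.** Cognitive reappraisal is the mechanism that the intervention is named for and the first outcome in Aim 3. Supportive Therapy serves as the control because it does not target it. A follow-up list that names medical burden, which is in no numbered aim, and leaves out reappraisal looks out of step with the trial's purpose. Suicidal risk appears in that list only as ideation, although the Background also speaks of behavior and patients can enter after an attempt. Satisfaction is set at three visits in Aim 2c, at the end of CRISP in the benchmark line, and is not mentioned in the follow-up sentence.

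If these were real conflicts, two things would be at stake. Staff working from the visit text might not collect an outcome that an aim needs. And an outcome with no fixed measure or visit could be defined after the results are known. Aim 3 is the only aim that compares effectiveness between the arms, so that would matter.

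**Working it through.** No formula applies. The visible text states no sample size, error rate, power or effect size, and the question does not depend on them. The check is to set each outcome in the aims against the follow-up sentence and then against the rest of the document.

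**Count.** Participant outcomes in Aims 2c and 3: satisfaction, reappraisal, suicidal risk = 3. Not named in the follow-up sentence: 2. Named in part: 1 (ideation, for suicidal risk). Constructs the sentence does name: depression, anxiety, medical burden, suicidal ideation = 4, of which 1 belongs to a numbered aim. The count is correct. Whether it shows a fault depends on whether the list is meant to be complete.

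**Is the list complete?** Its verb leaves it open. The section also gives direct evidence that it is not complete: the EEG tasks are study procedures mentioned in the payment text, and they are not on the list. Absence from the list is therefore weak evidence that something is not collected.

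**Satisfaction.**

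| Source | Arms | Times | Role |
|---|---|---|---|
| Aim 2c | 2 | 6, 12, 24 weeks | schedule |
| Benchmark line | CRISP | end of treatment | progress marker |
| Follow-up sentence | not stated | 6, 12, 24 weeks | examples of content |

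Aim 2c gives 2 arms × 3 visits = 6 arm-by-visit cells, at the same visits as FOLLOW-UP ASSESSMENTS. The benchmark line follows a completion target for CRISP participants only, and asks for scores from that arm at one time. If CRISP ends at about 12 weeks, which is an assumption suggested by the 12-week span of Aim 3 and the three-month focus in the Background, that is 1 of the 6 cells. If it ends at another time, it is one further collection. Neither case conflicts with Aim 2c.

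**Suicidal risk.** The Background gives its reason for stressing ideation: after a suicide-related admission, ideation is itself a known risk factor for suicide. Measuring ideation at follow-up is consistent with that. Whether the Aim 3 outcome also includes behavior, and on which scale, is not stated. The scale in the inclusion criteria is used there for admission status only.

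**Cognitive reappraisal.** Aim 3 covers 12 weeks, so 2 of the 3 visits (6 and 12 weeks) fall within it. No visible sentence names an instrument or task for reappraisal, or assigns it to a visit. The EEG tasks and the mention of levels of analysis may relate to it, but the text does not say so.

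**Where the detail could be.** Under OVERVIEW OF DESIGN only the label of Figure 1 remains. The RESEARCH ASSESSMENTS heading is followed directly by eligibility criteria. Other figures near Aim 2 are not shown, and the document ends in redacted blocks. A schedule of assessments could be in any of these places, or in an analysis plan that was not available.

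**The case for a change.** The best argument for a change is that an analysis plan governs how data are analysed, while an operations manual should say what is collected and when. On that view the manual should name the measure of the trial's own target mechanism, an unseen analysis plan is no excuse, and the repair is a few words in three places.

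Part of this stands. In the visible text reappraisal has neither a measure nor a visit, and the reach of suicidal risk in Aim 3 is left open. A reader would be helped by one sentence on each, or by a pointer to a schedule.

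The rest does not carry the argument to a change. The repair would correct no false statement, replace no rule and improve no method. It would add detail that may already exist in parts of the manual missing from this copy. Satisfaction does not support the case, because Aim 2c fixes arms and visits on its own. The concern about defining outcomes late would have force if the full manual and the analysis plan were known to be silent, and that cannot be established here.

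**Conclusion.** The concern does not call for a change. The follow-up sentence gives an open list that is shorter than the set of outcomes in the aims, and that is not a contradiction. Satisfaction is scheduled in Aim 2c at the same three visits, and the benchmark line is compatible with it. The emphasis on ideation has a stated reason.

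The remainder is small: two points of missing detail, namely the measure and visits for cognitive reappraisal and whether suicidal risk in Aim 3 covers behavior as well as ideation. Analysts would ordinarily settle both from the assessment schedule or the analysis plan. No bias, loss of power or uncollected outcome can be shown from the text.

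This rests on two assumptions: that the follow-up list is illustrative, which its wording and the EEG tasks support, and that the missing figures, redacted blocks or analysis plan hold the usual schedule and outcome definitions, which cannot be checked here.

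### Does giving the research assistant the follow-up assessments, the visit data and the patient summaries open the outcomes to knowledge of the arm?

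*Protocol*

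**What the plan says.** In FOLLOW-UP ASSESSMENTS the Protocol states: "Follow-up assessments are conducted by the WCM research assistant at 6, 12, and 24 weeks after the baseline". It adds that these assessments "include measures of depression and anxiety symptoms, medical burden, and suicidal ideation".

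DATA MANAGEMENT then lists who handles what:

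- Collection: "Data will be collected by the study RA at baseline and at follow-up assessments".
- Reporting to the principal investigator: "The RA will also be responsible for writing and presenting patient summaries to the PI".
- Reporting on therapy: "The therapist will complete updates on the progress of their therapy sessions".

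STUDY AIMS, Aim 2c, places "treatment satisfaction at 6, 12, and 24 weeks" among the acceptability measures, and Aim 2 is assessed in both conditions. Who administers the satisfaction measure is not said.

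Two places describe material for CRISP alone. BACKGROUND names the aids ("WellPATH personalized tablet app, written step-by-step plan, phone calls"), and INTERVENTION says that "at the end of treatment CRISP therapists provide to patients a personalized summary of treatment".

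Aim 3 compares CRISP with Supportive Psychotherapy on cognitive reappraisal and suicidal risk over 12 weeks.

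**The concern.** Two talking therapies cannot be masked from the patient or the therapist, so the credibility of a rated outcome rests largely on the assessor. Here the assessor's role is also the one that presents patients to the principal investigator. A reader used to case conferences will picture summaries that cover how therapy is going. Treatment satisfaction falls due at the same weeks as the symptom measures, and a patient asked about treatment could mention the tablet app or the written plan, which are described only for CRISP. An assessor who learned the arm at week 6 would then rate the same patient at weeks 12 and 24 with that knowledge.

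If that happened with interviewer-rated measures, any leaning toward CRISP would enter the between-arm effect size of Aim 3 directly, and a larger sample would not remove it. The visible text contains no statement on masking to set against this.

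**Working it through.** The Protocol gives no figure on this point, and its visible text has no sample size, standard deviation or test. The check is therefore mainly a reading of the sections side by side, followed by a look at what the only available arithmetic can show.

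**Step 1. Do the stated duties reveal the arm?** Conducting an assessment, recording its data and summarising a patient can all be done without knowing the allocation. The Protocol does not say that the summaries name the arm or describe therapy content. The sentence directly after the one on summaries gives progress reporting on sessions to the therapist, and nothing says that the RA receives those updates. On its face, the text assigns assessment material to one role and therapy material to another.

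**Step 2. What else would have to be true?** For the week-12 comparison to be biased through the satisfaction route, all of the following must hold:

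1. The RA administers or sees the satisfaction measure. This is not stated; it is inferred because no other collector is named.
2. The patient, while answering, mentions something specific to one arm. The measure is used in both conditions, so the questions themselves need not identify the arm.
3. The RA recognises the remark as belonging to that arm.
4. The later outcome is rater-scored or interviewer-administered. The Protocol does not say whether the follow-up measures are rated or self-completed.
5. The RA's knowledge moves the score in a consistent direction.

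The summary route needs a different opening link, that the summaries draw on therapy content, and then links 4 and 5. That opening link is not stated either.

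**Step 3. Do the time points line up?** Aim 3 ends at 12 weeks. The personalised treatment summary is handed over at the end of treatment. If treatment follows the 12-week course (an assumption), it could inform an assessor before week 24 but hardly before the week-12 assessment. It adds little to the comparison said to be at risk.

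**Step 4. Can masking be called absent?** OVERVIEW OF DESIGN consists, in the text at hand, of a figure label without the figure. Two figures in STUDY AIMS are also not shown, and six blocks after DATA MANAGEMENT are redacted. A design overview is a natural place for a statement on allocation and masking. The visible text does not say how patients are allocated to the arms either, so its silence on masking carries little information.

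**Step 5. What can be said about size?** Let q be the share of patients whose arm the RA knows, and b the shift in SD units when it is known. The bias in the standardised difference is then

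bias = q × b

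| q (assumed) | b (assumed) | bias |
|---|---|---|
| 0.25 | 0.1 SD | 0.25 × 0.1 = 0.025 SD |
| 0.50 | 0.2 SD | 0.50 × 0.2 = 0.10 SD |
| 1.00 | 0.3 SD | 1.00 × 0.3 = 0.30 SD |
| any | about 0 (self-completed measures) | about 0 |

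The arithmetic is correct, but neither input comes from the Protocol. The range shows what would follow if unmasking occurred and mattered. It gives no evidence that either happens.

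**The case for a change.** The strongest argument for the concern is that this document is an operations manual. Who rates, in what order, and what a summary may contain are matters of conduct that belong here and would not normally be left to a statistical analysis plan. A masked rater also needs a workflow that protects the mask, and the visible text sets none: no task order within a visit, no limit on summary content, no request that patients keep their treatment to themselves. Cheap safeguards exist, such as completing the symptom measures before the satisfaction measure.

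Part of this stands. The three duties do rest with one role, and assessor masking is a matter for this document. It is also true that the visible text does not say whether the RA is masked, and a sentence on it would help a reader judge Aim 3.

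The rest does not carry the point. The text fixes a role, not a headcount, so it does not establish that a single person holds all three duties for a given patient. A different task order or a narrower summary would replace no rule in the Protocol; these are preferences about a workflow that it does not describe. The summaries' content is unknown, so a limit on it might change nothing. In a population at risk of suicide, the RA's reports to the principal investigator may also carry safety information, so the cost of restricting them cannot be judged from this text.

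**Conclusion.** The concern does not hold. The Protocol gives the RA assessment, data collection and patient summaries, and gives reporting on therapy sessions to the therapist. Nothing in it says or implies that the RA knows the arm. The harm depends on a chain of steps that are not stated, and on treating masking as absent when the design overview is not shown and the closing text is redacted.

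No size can be put on it from the Protocol. The span from 0 to 0.30 SD rests wholly on assumed values for how often the arm becomes known and how far that shifts a rating, and it is about 0 if the measures are self-completed.

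The conclusion rests on two readings: that the summaries are not stated to include therapy content, and that missing or redacted material cannot be counted as a gap in the plan. If the complete document showed that the RA is told the arm and that the outcomes are interviewer-rated, the question would have to be reopened. On the present text, the most that remains is a clarification, whether and how the RA is masked. No stated rule needs correcting.
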